6.7 Outcome Measures

Primary Outcome Measures – success criteria:

- Monitor tolerability for tVNS
 - Symptom severity scores of mild or moderate in less than 1/3 of participants able to report symptoms (based on Likert Scale 1-5; 1 representing no issues; 5 representing severe symptoms)
- Assess study feasibility
 - recruit >1 patient per month of recruitment
 - >80% of recruited patients completing primary outcome measures at 4 weeks follow up

These outcome measures will be collected during the participants inpatient stay over the intervention period using a data collection proforma (appendix) and taken from recruitment records kept contemporaneously. Safety assessment of SAEs / AEs will be collected each intervention day by our research team.

Secondary Outcome Measures:

- Monitor safety criteria for tVNS
 - No SAEs reported to tVNS
 - Unexpected AEs in less than 1/3 of participants
- Explore clinical outcomes including:
 - rates of clinical or radiological DCI (%)
 - inpatient mortality (%)
 - inpatient length of stay (days)
 - rate of complications: seizures, hyponatraemia, rebleed, hydrocephalus (%)
- Outcome measures using questionnaires on discharge and at 1-month
 - Disability assessment: modified Rankin Score, Barthel Index
 - Assess frequency and severity of headache: Likert scale
- Explore mechanisms of action:
 - Inflammatory markers at baseline and 5 days
- o Explore response to tVNS:
 - Near-infrared cerebral spectroscopy
 - Heart rate variability
 - Pupillary reactivity

These will be measured during the inpatient hospital stay up until discharge (Figure 1).

- Outcome measures using questionnaires at on discharge and at 4 week follow-up
 - Disability assessment: modified Rankin Score, Barthel Index
 - Assess frequency and severity of headache: Likert scale (1-10 where 1 is non-existent and 10 is extremely severe)
- Explore mechanisms of action measured at baseline and at the end of intervention (5 days):
 - Inflammatory marker analysis at baseline and 5 days (IL-1B, IL-6, IL-10, TNFa)
 - Concurrent WCC, CRP and infection will be recorded at these time points as these may confound results
- o Explore response to tVNS:
 - Near-infrared cerebral spectroscopy
 - Heart rate variability (HRV) parameters using a commercially available heart rate monitor (SDRR standard deviation of the inter-beat-interval ms; RMSSD the root mean square of successive differences between heartbeats ms; LF power power of HRV distributed in the low frequency (0.04 0.15) band indicative of sympathetic nervous activity; HF power power of HRV distributed in the high frequency (0.15 0.4) band indicative of parasympathetic nervous activity; LF/HF ratio) 10-12
 - Pupillary reactivity (constriction and dilatation amplitudes mm; constriction speeds ms, latency ms)¹³. Confounders including eyedrops that may influence pupil size will be recorded

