Is transcutaneous nerve stimulation a tolerable and feasible intervention to potentially improve clinical outcomes in aneurysmal subarachnoid haemorrhage (aSAH)?

3. Abstract/Summary

Background

Subarachnoid haemorrhage (SAH) is a type of brain bleed, which can be complicated by issues including delayed cerebral ischaemia (DCI) which causes stroke like symptoms, such as weakness, in up to 30% of patients. Current treatments for DCI focus on improving blood supply but fail to address other important factors including reducing inflammation.

Stimulation of a nerve in the neck called the vagus nerve, which can be done through the skin (transcutaneous vagus nerve stimulation, tVNS) is known to relax blood vessels and reduce inflammation and is approved in other conditions such as epilepsy.^{3,4} In animals, vagus nerve stimulation improves survival after aSAH, and is being studied in humans to reduce headaches after aSAH.^{5,6}

There is a theoretical role of tVNS in improving outcome after aSAH. We aim to study whether tVNS is tolerated, and feasible in aSAH.

Methods

This is a single centre, pilot randomised controlled trial (RCT); the participants will receive either tVNS or 'sham' tVNS, twice daily for 45 minutes for 5 days. We will monitor tolerability (symptoms) and feasibility (recruitment rates) for recruited patients. Secondary outcomes will include rates of side effects, complications from SAH, outcomes on discharge and 4 week follow up, and exploration of mechanisms of action and response to tVNS including levels of serum inflammatory markers (IL-1B, IL-4, IL-6, IL-10 and TNFa), functional near infra-red spectroscopy (f-NIRS), heart rate variability (HRV) and pupillary light reactivity (PLR).

Results

Rates of complications, side effects and recruitment will be reported descriptively and we will undertake simple between-group statistical analyses on secondary outcome measures. If proven to be tolerated and feasible, this study will provide the basis for a future larger trial design.

4. Aims of the Study

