The aims of the study will be to conduct a pilot RCT to investigate whether tVNS is a tolerable and feasible treatment for acute aSAH. To understand this we will recruit participants who have recently undergone acute securing procedures follow acute aSAH (coiling or clipping of aneurysm) to a 5 day programme of intervention (active tVNS vs sham) and collect outcome data (primary and secondary as per outcomes section). We will evaluate whether pre-defined success criteria are achieved for tolerability and feasibility and explore signals of effect on clinical outcome measures and mechanistic measures. Non-invasive vagal nerve stimulation has not been

studied in the acute period following aSAH outside of the remit of reducing headache. This should offer critical insights as to whether this intervention has potential to take forward to a larger phase 2/3 clinical study.

5. Background

Delayed cerebral ischaemia (DCI) is a multifactorial sequela of aneurysmal subarachnoid haemorrhage (aSAH) which occurs in up to 30% of patients, usually within 14 days of ictus. Diagnosis is by means of clinical and radiological assessment of a new neurological deficit in the absence of other causes. Alongside rebleeding, DCI is the strongest predictor of in-hospital mortality after aSAH and has a significant impact on morbidity.

The pathophysiology of DCI is complex and poorly understood, but emerging evidence supports a multifactorial model which includes arterial vasospasm, inflammatory processes, localised coagulopathy, and failure of cerebral autoregulation – this represents a vasculopathic progress, rather than purely vasospasm. Current management strategies for DCI focus on overcoming vasospasm, primarily by inducing hypertension, although this fails to address other important factors in the disease pathophysiology such as the inflammatory process. Interventions that target a multiple pathophysiological pathways may offer greater clinical benefits.

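### As worded, the primary tolerability criterion does not count severe symptom scores, so a participant who worsens from moderate to severe helps it to be met

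*Protocol*

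**What the plan says.** Protocol section 6.7 lists tolerability first among the primary success criteria and defines it as "Symptom severity scores of mild or moderate in less than 1/3 of participants able to report symptoms". It gives the scale as a five-point Likert item, with "1 representing no issues; 5 representing severe symptoms". The synopsis (section 1) repeats the criterion without the scale anchors. The text shown gives no labels for scores 2, 3 and 4. Section 6.7 says the primary data are collected "using a data collection proforma (appendix"), but that appendix is not in the text at hand.

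The other two primary criteria concern the recruitment rate and completion of outcome measures. Neither uses the severity score. The harm limits are secondary: no serious adverse event attributed to tVNS, and "Unexpected AEs in less than 1/3 of participants".

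On how the criterion is used, section 4 states: "We will evaluate whether pre-defined success criteria are achieved for tolerability and feasibility". Section 3 adds: "If proven to be tolerated and feasible, this study will provide the basis for a future larger trial design". Section 7.2 says the primary outcomes are reported descriptively as proportions.

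**The concern.** A tolerability rule should never become easier to satisfy when a participant's symptoms get worse. This one does. It puts an upper limit on the share of reporters in two middle categories and none on the category above them. A participant who moves from moderate to severe leaves the numerator and stays in the denominator.

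This is the trial's only primary criterion for tolerability, and it feeds the decision on whether to go on to a larger trial. A pass that arises because some symptoms were severe would support the wrong conclusion. The protocol itself fixes the rule, in two places. An analysis plan that counted severe scores would therefore be departing from the protocol's wording, not filling in a detail left open.

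**Working it through.** The protocol gives no calculated figure for this criterion, so there is none to reproduce. The check applies the rule literally.

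**Inputs**
- Counted scores: mild or moderate (sections 1 and 6.7).
- Threshold: strictly less than 1/3 of participants able to report (same places).
- Scale: 1 = no issues, 5 = severe (section 6.7).
- Number of reporters, n: not stated. I use 10, 15, 20 and 30 as an assumed range. The planned total is 30. The synopsis gives 15 per arm, and the 2:1 randomisation in section 6.10 would give 20 and 10. The conclusion does not depend on which applies.

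**Rule as written**

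Pass if M/n < 1/3, where M is the number of reporters with a mild or moderate score. The number of severe scores, S, does not appear.

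**Step 1: what passes.** The largest M with M/n < 1/3 is 3 of 10, 4 of 15, 6 of 20 and 9 of 30.

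**Step 2: move one participant from moderate to severe.**

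| n | Before: all counted scores moderate | After: one worsens to severe |
|---|---|---|
| 10 | 4/10 = 40.0%, fail | 3/10 = 30.0%, pass |
| 15 | 5/15 = 33.3%, fail (not below 1/3) | 4/15 = 26.7%, pass |
| 20 | 7/20 = 35.0%, fail | 6/20 = 30.0%, pass |
| 30 | 10/30 = 33.3%, fail (not below 1/3) | 9/30 = 30.0%, pass |

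In each row symptoms are worse on the right, and the result changes from fail to pass.

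**Step 3: the extreme case.** If every reporter scores 5, M = 0 and 0/n = 0 < 1/3. The criterion is met for any n. This is a limiting case to show the logic, not a forecast.

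**Step 4: do the other limits catch it?** Take a symptom that is severe, expected and non-serious.
- It is not a serious adverse event, so the first secondary limit is not triggered.
- It is not unexpected, so the second is not triggered.
- The recruitment and completion criteria do not use severity.

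**Step 5: the two likely intentions are different rules.** Take 20 reporters with 13 scoring no issues, 4 mild, 3 moderate and none severe.
- Mild or worse: (4 + 3 + 0)/20 = 35%, fail.
- Moderate or worse: (3 + 0)/20 = 15%, pass.

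Adding *or worse* therefore settles the rule only if the cut is also stated.

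**Step 6: the repaired rule.** With a cut at moderate or above, chosen only to illustrate, 7 moderate gives 7/20 = 35% and 6 moderate plus 1 severe gives (6 + 1)/20 = 35%. Both fail, so worsening no longer helps.

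**The case against.** The strongest reply is that this is a slip of wording and that nobody meant to exempt severe scores. If even mild symptoms count against the device, the natural reading is a floor: anything at least that bad. In a small pilot with descriptive reporting, a pass produced by severe scores would be plain to see. Figure 2 in section 6.10 schedules tolerability reporting at Visits 1 to 4, at discharge and at 4 weeks, so the scores would be recorded. Stimulation intensity is also limited by tolerance or pain (sections 1 and 6.9), which makes many severe scores less likely.

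Most of this stands, and it limits the consequence. It does not cure the rule. The reader must supply the floor reading, it has two versions that can disagree (Step 5), and section 4 applies the criterion as pre-defined.

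Some stronger readings are tempting but not supported:

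- *The cut would have to be chosen after the data are seen.* The proforma and any SAP are not shown, and either could fix the cut or label scores 2 to 4. All that can be said is that the protocol text at hand does not.
- *The chance of a false pass can be quantified.* The protocol gives no symptom rates, so any such probability rests on invented ones. A case with 20 active reporters would also need the 2:1 allocation and every active participant able to report, against 15 per arm in the synopsis.
- *The denominator is contradictory.* Section 3 says "We will monitor tolerability (symptoms) and feasibility (recruitment rates) for recruited patients", but that sentence summarises tolerability and feasibility together. The criterion's own lead-in, on tolerability for tVNS, points to the active arm. The analysis set is commonly left to the SAP.
- *Stopping for intolerance goes unseen.* Figure 2 schedules reporting of tolerability and of the duration of intervention delivered, and section 6.8 records reasons for dropout.
- *Withdrawals distort this rule.* Sections 6.8 and 10.1 differ on data from participants who withdraw, but that touches every outcome and is a separate matter.

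**Conclusion.** The criterion is wrong as written and should be corrected. Severe scores do not count against tVNS, and one participant worsening from moderate to severe can change the result from fail to pass: 7/20 (35%) against 6/20 (30%). The conclusion rests only on the stated wording and on 5 meaning severe. It needs no assumed symptom rate, no labels for scores 2 to 4 and no particular allocation ratio. The 20 reporters are an illustration, and the same reversal occurs at 10, 15 and 30.

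The practical consequence is moderate. The intent is probably mild or worse, or moderate or worse, and descriptive reporting should reveal severe scores. A reader might infer that the plan hides severe symptoms, or that a false pass is likely. The documents support neither. What they show is a pre-defined success rule that worse symptoms can help to meet.

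**What to change.** Reword the criterion in the synopsis and in section 6.7 along these lines: *tolerability is met if fewer than 1/3 of participants able to report symptoms have a score at or above [stated cut]*. The sponsor should choose the cut before data are seen, give it as a number on the 1-5 scale and make it match the proforma. Any cut from 2 to 5 written as *at or above* ensures that a score of 5 always counts.

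The change is to wording only and needs no new data item, since the scores are already planned. The cost is that the criterion becomes harder to meet, because severe scores now count against it.

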13.	Taking the Work Forward	. 20
14.	Intellectual Property (IP)	. 20
15.	Costing Schedule	. 21
16.	Funding Arrangements	. 21
17.	References	21

1. Study Synopsis/Profile

Study title	Investigating the tolerability and feasibility of transcutaneous vagus nerve stimulation following aneurysmal subarachnoid haemorrhage				
Study short title	tVNS in aSAH				
Study design	Two-arm randomised controlled trial				
Study participants	Inclusion criteria:				
	 Age >18 Admitted to STH neurosurgery Confirmed aneurysmal SAH on vascular imaging Within 5 days of 'Securing' aneurysm (i.e., successfully coiled or surgically following rupture) 				
	Exclusion criteria:				
	 Current or prior use of a vagus nerve stimulation Symptomatic bradycardia or PPM insertion Complete heart block Implantation of any other electrical stimulator (e.g. DBS) 				
Planned sample size	30 participants (15 in each arm)				
Planned study period	36 months				
Planned recruitment period	24 months				
Study assessments	 Deliver TVNS using the parasym device for 45 minutes twice daily for 5 days following aSAH intervention (coiling or clipping) Pulse width 25ms, frequency device standard (25 Hz), at maximum tolerated intensity, or 				

	20MA for patients who cannot report the maximum tolerated intensity • Clinical follow-up on discharge and at 1 month				
Objectives	s Primary				
•	To establish the tolerability, and feasibility of tVNS in patients following aSAH, including;				
	 Monitor tolerability for tVNS Symptom severity scores of mild or moderate in less than 1/3 of participants able to report symptoms Assess study feasibility recruit >1 patient per month of recruitment >80% of recruited patients completing primary outcome measures 				
	Secondary				
	 Monitor safety criteria for tVNS No SAEs reported to tVNS Unexpected AEs in less than 1/3 of participants Explore clinical outcomes including: rates of clinical or radiological DCI inpatient mortality inpatient length of stay Rate of complications: seizures, hyponatraemia, rebleed, hydrocephalus Outcome measures using questionnaires on discharge and at 1-month Disability assessment: modified Rankin Score, Barthel Index Assess frequency and severity of headache: Likert scale Explore mechanisms of action: Inflammatory markers at baseline and 5 days Explore response to tVNS: 				
	 Near-infrared cerebral spectroscopy Heart rate variability Pupillary reactivity 				

2. Research Questions

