6.6 Recruitment

Potential participants with aSAH will be identified on admission to neurosurgery at RHH and approached about the study by the clinical treating team on the basis of convenience sampling. If they are interested in the study, they will be provided with an information sheet again and the opportunity to discuss the study with a member of the research team. If they are willing to take part in the study written informed consent will be obtained, after a screening consent support tool is used to ensure the patient had adequate comprehension.

Capacity to consent to the study would be determined by the treating clinical team and confirmed by the research team according to the principles of the mental capacity act (MCA, 2005). Where the patient lacks capacity to consent (including sedated/intubate patients), a personal or nominated consultee can provide advice on what they feel the patients' wishes would be if they had capacity. The treating clinical team would

introduce the study to the consultee and an information leaflet given to them. The consultee would then have the option to sign a consent form if they believed the patient would agree to participate. In accordance with the MCA 2005, ongoing consent or assent would be sought from the individual or consultee at each study visit, before any research activity at the that visit is undertaken. Consultees may advise at any point that they believe the person's wishes about participation have changed and they should therefore be withdrawn from the study. Agitated patients will not receive the intervention if they are unable to tolerate it.

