6.8 Subject Withdrawal, Breaking the Blind and Trial Discontinuation Rules

Participants will be advised that they can withdraw from the study at any time without giving a reason and without this affecting their clinical care. Any data already collected will be analysed with permission from the patient. A member of the research team will confirm the patient is happy to continue with the longitudinal study at their clinical follow up appointments.

We will record data including number of patients admitted with aneurysmal SAH, number eligible, number recruited, dropout rates, and reasons for these. Participants will be given the opportunity to get involved in a public patient involvement group (PPI) at completion of the study.

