6.9 Intervention

We are using tVNS settings that are widely used in other neurological conditions (epilepsy, migraine)¹⁴. These include:

- o Pulse width 25ms
- Frequency device default (20 or 25Hz)
- Intensity below pain threshold.
- Frequency 45 minutes twice daily. On the basis of similarity to other studies, practicalities on the ward and clinical scenario

We have chosen a duration of 5 days based on the usual clinical pathway of inpatient management at the Royal Hallamshire Hospital, and have chosen to deliver the treatment twice daily to optimise the dose. This is a pilot study with feasibility outcomes and as such we will be exploring the feasibility of this treatment regimen.

The Parasym Device will be applied to the left tragus (figure 1) as this is the most common site for tVNS delivery in neurological studies and is associated with few afferents to the heart.

The intervention is aimed at supplementing routine clinical care, and as such, the doses of tVNS can be interrupted for care activities (therapy sessions, examinations, assessments etc) and resume afterwards. The overall minute duration will aim to remain 45 minutes twice daily.

[figure not shown]

Figure 1. Anatomy of the ear and the tragus (a). Parasym attached to the tragus (b)

The active intervention will be compared to sham tVNS where the vagal nerve stimulator will be attached to the earlobe instead of the tragus, in keeping with evidence that this does not cause vagus nerve stimulation and is in line with sham methods used in other studies. We do not anticipate that patients will have the intervention long enough to become familiar with the common sensations associated with true tVNS intervention. At the end of the intervention period, participants will be asked if they thought they had received true of sham tVNS to understand the blinding ability of the sham.

We will use the FNIRS Lumo ecosystem (Gower labs) to assess cerebral blood flow in the frontal lobes. We will complete a protocol where 6 optodes are placed bilaterally over the frontal and prefrontal cortices. We will complete and record resting state signals of oxyhaemoglobin and deoxyhaemoglobin for 5 minutes while patients are layed in bed with their eyes closed (or wearing an eye patch). Following the 5-minute rest phase, vagal nerve stimulation or sham stimulation will start

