6.10 Study Protocol

Patients (or their representatives if they lack capacity) who are eligible for entry into the will be approached by the treating clinical teams with information about the study. Those who are interested will be given an information sheet and time to consider the study. Those keen to participate will sign a consent form (or assent form for those that lack capacity) and baseline outcome measures will be performed.

Enrolled participants will be issued with a study number and randomised 2:1 (SealedEnvelope Ltd) stratified according to age (<65 and ≥ 65 years). They will then receive either active tVNS stimulation (tragus) or sham (earlobe), twice daily for 45 minutes per session for 5 days. We do not anticipate discharges from hospital earlier than 5 days as this is not routine practice in the neurosurgical unit.

Primary outcome measures of tolerability and feasibility will be collected daily by researchers delivering the intervention, and secondary outcome measures will be collected at the end of intervention or on hospital discharge as detailed in figure 2.

Following discharge from hospital participants will return for follow up clinic assessment at 4 weeks where questionnaire measures of functional recovery and adverse event reporting will be undertaken. After this the participants involvement in the study will be complete.

Figure 2: Study Schedule for Outcome Measures

	Baseline visit	Visit 1	Visit 2	Visit 3	Visit 4	Visit 5 (EOT)	discharge	At 4 weeks
Eligibility screening	Х							
Informed consent	Х							
Randomisation	Х							
Socio- demographic data	X							
Clinical data collection	X						X	
Questionnaires: Disability - mRS, BI, headache likert scale	X						X	X
Reporting of side effects, adverse events and tolerability		X	X	X	X		X	X
Intervention reporting – settings delivered, duration of intervention		X	X	X	X			
Pupillometry + recording of prescribed eye drops	X					X		
Heart rate variability	X					X		
fNIRS	Х					X		
Monitor blood test results (secondary outcome measures), collection of data on WCC/CRP and infection status	Х	X	X	X	X		X	
Inflammatory marker analysis	X					Х		

EOT = End of treatment; BI = Barthel Index;

fNIRS = Functional near infra-red spectroscopy

7. Data Management

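### The primary tolerability criterion counts only symptom scores in participants able to report, so treatment withheld, permanently stopped or withdrawn for intolerance does not count in itself

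*Protocol*

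**What the plan says.** The tolerability line among the primary success criteria in section 6.7, repeated in the synopsis, is "Symptom severity scores of mild or moderate in less than 1/3 of participants able to report symptoms", on a 1 to 5 scale. Section 6.10 adds: "Primary outcome measures of tolerability and feasibility will be collected daily by researchers delivering the intervention".

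The protocol expects that some patients will not be treated because they cannot tolerate the device. Section 6.6 states: "Agitated patients will not receive the intervention if they are unable to tolerate it". The same section lets a consultee advise withdrawal. Section 6.8 says that the trial will record "dropout rates, and reasons for these", and Figure 2 has a row for the settings and duration delivered. None of these records is tied to a success criterion for tolerability.

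Patients without capacity, including sedated or intubated patients, may be enrolled. The synopsis (Study assessments) sets the intensity at the maximum tolerated, or "20MA for patients who cannot report the maximum tolerated intensity". Section 6.9 says only that intensity stays below the pain threshold.

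Two other criteria in section 6.7 touch these patients. Safety (secondary) covers SAEs and unexpected AEs. Feasibility (primary) requires more than 80% of recruited patients to complete the primary measures at 4 weeks.

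**The concern.** A patient who cannot bear the device and is therefore left untreated is the plainest case of intolerance. The rule does not see that event. It sees a symptom score, and only from someone who can give one. A reporter who stops may already have a counted score. A participant who never regains the ability to report cannot have one.

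Those non-reporters are also the ones whose intensity is not set by their own feedback. Section 10.1 justifies enrolling patients who lack capacity by their likely large share of the aSAH population and by the wish for generalisable results. The tolerability line can be met without any information from the part of that group that never reports.

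The criterion is one of the few pre-set conditions for taking tVNS to a larger trial, so what it counts affects what a pass means.

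**Working it through.** The protocol gives no derivation for the 1/3 limit and no expected rate of intolerance, so there is no figure to reproduce. The check asks which events and which patients can move the result.

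**Inputs**
- Limit: less than 1/3, so k counted participants among n reporters pass if 3k < n (section 6.7). I take a counted score to be whatever the rule counts.
- Active arm: the synopsis says "30 participants (15 in each arm"), while section 6.10 says "Enrolled participants will be issued with a study number and randomised 2:1". I show both, taking 2:1 as 20 active and 10 sham. The larger arm is not named, so this is an assumption.
- Arm: section 6.7 names none. Applying the rule to the active arm is an assumption, and the pooled figure is given as well.
- Share able to report: not stated. Section 7.1 expects about 50% to be unable to complete questionnaires. I use one half as a stand-in, with a range of one third to two thirds.

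**Step 1: the largest passing count**

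| Active arm | Share reporting | Reporters n | Largest passing k | Next count fails | Non-reporters |
|---|---|---|---|---|---|
| 15 | 1/3 | 5 | 1 (20%) | 2/5 = 40% | 10 |
| 15 | 1/2 | 8 (7.5 rounded up) | 2 (25%) | 3/8 = 37.5% | 7 |
| 15 | 2/3 | 10 | 3 (30%) | 4/10 = 40% | 5 |
| 20 | 1/3 | 7 (6.7 rounded) | 2 (28.6%) | 3/7 = 42.9% | 13 |
| 20 | 1/2 | 10 | 3 (30%) | 4/10 = 40% | 10 |
| 20 | 2/3 | 13 (13.3 rounded) | 4 (30.8%) | 5/13 = 38.5% | 7 |

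With 7 reporters of 15 instead of 8, the limit is still 2. Pooled over both arms at one half, n = 15 and k is at most 4 (26.7%), because 5/15 = 33.3% is not less than 1/3.

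**Step 2: what non-reporters contribute.** They are in neither k nor n, so no event among them changes the result. As a logical bound at one half, a just-passing result is compatible with (2 + 7)/15 = 60% or (3 + 10)/20 = 65% of the active arm having either a counted score or treatment ended for intolerance.

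**Step 3: the same limit over all active participants.** It allows 4/15 (26.7%) or 6/20 (30%). Starting from the just-passing counts, two further participants whose treatment ended for intolerance give 4/15 and still pass, while three give 5/15 = 33.3% and fail. Under 2:1, three give 6/20 and pass, while four give 7/20 = 35% and fail.

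**Step 4: whether the other criteria close the gap.** More than 80% of 30 means at least 25 completers, since 24/30 = 80% is not enough. Six withdrawals that lead to non-completion would therefore fail feasibility. Up to five would pass, a patient left untreated can still complete follow-up, and a failure does not show intolerance as the cause. The AE criterion is secondary, and refusal or agitation need not be recorded as an unexpected AE.

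**The case against.** The strongest reply is that intolerance is not invisible. Symptoms are collected daily, so many reporters who stop will already have a score. Dropout reasons and delivered duration are recorded, AEs cover everyone, and withdrawals can reach the completion criterion. Primary outcomes are reported descriptively, and a table of stops by arm could be left to an analysis plan. All of this is right, and it limits the point to the word count: the information exists but does not enter the tolerability rule. That rule is fixed in the protocol, so changing what it counts is not merely a matter of later analysis detail.

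Three stronger readings are tempting and not supported.
- *That patients at fixed 20 mA get no tolerability result.* The synopsis describes those who cannot report a maximum tolerated intensity, and section 6.7 leaves out those who cannot report symptoms. The protocol does not equate the two groups. Section 10.1 foresees capacity returning during the intervention period, so some may report later.
- *That the criterion will understate intolerance by a known amount.* It can, but need not. With 8 reporters and a true counted rate of 20%, the chance of exactly two counted cases is 28 x 0.2^2 x 0.8^6 = 0.29. That is not the chance of a reversal, which also needs an intolerance stop in someone without a counted score. The protocol gives no rate for that. It also expects very few missing primary data.
- *That every shortened session shows intolerance.* One short session in ten is weak evidence, and section 6.9 expects interruptions for care.

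One further caution stands. In non-reporters the staff judge the reason for stopping, in a single-blind trial, and agitation may come from the bleed.

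**Conclusion.** The point holds as a gap in a stated decision rule. The only tolerability criterion is a symptom score among participants able to report. Treatment withheld, permanently stopped or withdrawn for intolerance does not count in itself, and participants who never report are outside it. They are covered only by AE/SAE reporting and, if they do not complete, indirectly by the completion criterion.

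The sizes rest on three assumptions: the rule applies to the active arm, half can report, and active is the larger arm under 2:1. The 60% and 65% are bounds on what the rule permits, not expected effects. That the rule ignores non-reporters needs no assumption about rates. No number in the protocol is wrong. The change is worth making because it is cheap and makes a pass mean more.

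**What to change.** In section 6.7:
- Keep the symptom-score criterion for reporters.
- Add that any participant allocated to active tVNS, reporting or not, counts as not tolerating if treatment is withheld after randomisation, permanently stopped or withdrawn because of symptoms or inability to tolerate it.
- Do not count a single shortened session, routine titration or the interruptions of section 6.9 ("the doses of tVNS can be interrupted for care activities").
- Report the proportion not tolerating for all active participants, and separately for those at fixed 20 mA, with sham beside each. Read the tolerability result together with it against the existing limit: at most 4/15 or 6/20, according to the allocation that applies.

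The cost is a few sentences and a recorded reason whenever treatment is withheld or ended. Dropout reasons and delivered duration are already collected, and the proforma in the appendix, which is not shown, may already hold such a reason. The downside is that the figure may be less favourable, and in non-reporters it depends on staff judgement. The sham figure is therefore needed to show how much of it would occur without vagal stimulation.
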